5.2.1.2 Timing second PSMA-PET/CT – hormonal therapy response

Second PSMA-PET/CT needs to performed 2 months after start of hormonal therapy (+/- 1 week). As per guidelines recommendations, upfront therapy needs to be started <3 months after start of hormonal therapy.

5.2.1.3 Timing third PSMA-PET/CT – upfront therapy response Third PSMA-PET/CT needs to be performed 2 months after start of upfront therapy (+/- 1 week).

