1. INTRODUCTION AND RATIONALE

In men with newly diagnosed metastasized prostate cancer (i.e. metastatic hormone-sensitive prostate cancer; M+HSPC) who start on androgen deprivation therapy, a personalized approach towards choosing upfront additional therapy is required. PSMA-PET/CT early response has the potential to stratify patients who will best respond to chemotherapy or androgen-receptor targeted agents (ARTA).

In 2019, 15% of 13,000 prostate cancer (PCa) diagnoses in The Netherlands was already in the metastasized stage at first detection (~1,950 cases/year).(IKNL 2020) In M+HSPC, palliative androgen-deprivation therapy (ADT) is the backbone of therapy, usually a LHRH agonist.(Cornford 2019) The condition and associated treatments have a detrimental impact on quality of life (QoL).(Holm 2018) In recent years, different therapies have been found to have a favourable impact on overall survival (OS) when initiated directly upfront (which should be started <3 months after diagnosis) in combination with ADT, revolutionizing treatment for M+HSPC. These options include very different types of agents; chemotherapy (i.e. docetaxel) or novel androgen-receptor targeted agents (ARTA; such as: CYP-17 inhibitor: abiraterone, or competitive inhibitors of the androgen-receptor: apalutamide, enzalutamide).(James 2016, Sweeney 2015, James 2017, Fizazi 2017, Chi 2019, Davis 2019, Armstrong 2019). Although the favourable effect on OS of these drugs when added to ADT monotherapy is similar in the M+HSPC setting on a group level (docetaxel chemotherapy: hazard ratio OS 0.61-0.78; ARTA: hazard ratio 0.62-0.67), there are important differences in costs, treatment burden, side-effects, and impact on QoL.(Hird 2020) Also, the choice for a specific therapy in first line for M+HSPC influences the effectiveness of treatments when the castration-resistant phase of PCa (CRPC) is reached (after median 18 months).(deWit 2020) Currently, docetaxel chemotherapy is mostly used as a first line treatment in addition to ADT.(Kuppen 2019)

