2. OBJECTIVES

The primary objective of the current research proposal is to assess whether PSMA-PET/CT early response assessment (between start of upfront therapy and after 2 months of upfront therapy) is associated with treatment success (defined as time to development of CRPC). This may allow for individualized treatment planning in newly diagnosed M+ HSPC patients, who have started on ADT and receive additional upfront therapy (Figure 1).

By performing PSMA PET/CT at fixed time points during ADT and upfront therapy treatment, information is collected on the imaging–based response to treatment. Analysis of the value of PSMA-PET/CT will be assessed by predictive modelling, taking the following predictive factors into account: PET findings, PSA at diagnosis, pathological Gleason score, tumour load, and PSA early response.

The secondary objectives include:

- Predictive value of baseline PSMA-PET/CT imaging on time to development of CRPC.
- Predictive value of early response to ADT only (which is standard of care during first 2-3 months of therapy; upfront therapy needs to be started within this timeframe) on time to development of CRPC.
- Analysis of response in different subgroups of patients: high versus low tumour load, high versus low PSA, high versus low Gleason score, <median versus >median age at diagnosis.

* Primary predictor: Upfront therapy PSMA response

Fig. 1 PET-MaN study design. (SOC = standard of care) Imaging will include PSMA-PET/CT at standardized time points (instead of at progression / on indication only): 1st baseline, 2nd after 2 months of hormonal therapy (ADT), and 3rd after 2 months of upfront therapy (for docetaxel, this is between 3rd and 4th cycle (out of 6)).

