5. METHODS

5.1 Study parameters/endpoints

5.1.1 Main study parameter/endpoint

Main parameter:

- Response to upfront therapy on PSMA-PET/CT based on PERCIST (PET Response Criteria In Solid Tumours).

PERCIST consists of a set of rules to interpretate solid tumor response on the PET/CT originally based on the FDG-PET/CT (O 2016, Fanti 2019). It looks at the tumor uptake of the PET tracer also expressed as the standardized uptake value (SUV). It divides tumor response based on the perceptual change in SUV between two (in our case) PSMA PET/CT's and the change in the amount of tumor lesions (see table 1). For the notation you also need to include the amount of time between the two PET scans. For example (35% increase, 4 weeks, five new lesions).

Table 1

Response	PSMA PET/CT interpretation
Complete response (CR)	Complete resolution of PSMA-tracer uptake in all
	lesions
Partial response (PR)	More than or equal to 30% reduction of SUV and an
	absolute drop of 0.8 SUV units
Progressive disease (PD)	More than or equal to 30% increase in SUV and
	absolute increase of 0.8 SUV units, or appearance of
	new lesions with PSMA-tracer uptake
Stable disease (SD)	Not quality for CR, PR, or PD

NB: lesions with prior radiation treatment (e.g. symptomatic bone metastasis) will not be accounted for in the PERCIST response evaluation.

Main endpoint:

- Time since start ADT to development of castration-resistant disease (CRPC). CRPC is defined by EAU guidelines (Cornford 2020) as:

Castrate serum testosterone <50 ng/dL or 1.7 nmol/L plus either:

- a. Biochemical progression: Three consecutive rises in PSA at least one week apart, resulting in two 50% increases over the nadir, and a PSA >2 ng/mL, or:
- b. Radiological progression: The appearance of new lesions: either two or more new bone lesions on skeletal scintigraphy or a soft tissue lesion on CT using RECIST (Response Evaluation Criteria in Solid Tumours) or on (PSMA-)PET/CT-imaging using PERCIST (PET Response Evaluation Criteria In Solid Tumours) (Fanti 2020, Boellaard 2015).

Symptomatic progression alone must be questioned and subject to further investigation. It is not sufficient to diagnose CRPC.

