5.1.2 Secondary study parameters/endpoints

- Predictive value of baseline PSMA-PET/CT imaging on time to development of CRPC.

- Predictive values of early response to ADT therapy on PSMA PET/CT (i.e. response between first and second PSMA PET/CT) according to PERCIST (PET Response Criteria In Solid Tumours).
- Predictive values of response to upfront therapy on PSMA-PET/CT (i.e. response between second and third PSMA PET/CT) according to PERCIST (PET Response Criteria In Solid Tumours).
- Analysis of response in different subgroups of patients: e.g. high versus low tumour load, high versus low PSA, high versus low Gleason score.
- -Time to initiation of second line therapy after castration-resistant disease has been found.

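### The second scan is timed from the start of ADT, not from the first upfront dose, so the scan 2 to scan 3 change does not reliably measure response to upfront therapy

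*Combined protocol and SAP*

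**What the plan says.** - **What should be measured.** Section 2 describes the early response of primary interest as lying "between start of upfront therapy and after 2 months of upfront therapy".
- **What is measured.** Section 5.1.2 takes response to upfront therapy from the scans themselves: "i.e. response between second and third PSMA PET/CT".
- **When scan 2 is taken.** Sections 3, 5.2 and 5.2.1.2 all place it 2 months after ADT start, plus or minus 1 week.
- **When scan 3 is taken.** Section 5.2.1.3 places it 2 months after the start of upfront therapy, plus or minus 1 week.
- **When upfront therapy may start.** Section 5.2.1.2 gives a latest time only: "upfront therapy needs to be started <3 months after start of hormonal therapy". Section 1 counts from a different date: "which should be started <3 months after diagnosis". Section 2 comes closest to an earliest time, in describing ADT alone: "which is standard of care during first 2-3 months of therapy; upfront therapy needs to be started within this timeframe".
- **What the model contains.** The first Cox model in section 7.1 has six factors, one of them PSMA response to hormonal therapy. The second adds PSMA response to upfront therapy. Neither has a term for the time from scan 2 to the first upfront dose or for the time between scans. Section 5.1.1 does ask for the scan interval, but only when the response is reported: "For the notation you also need to include the amount of time between the two PET scans".

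**The concern.** The defined predictor and the measured one agree only if scan 2 falls at the start of upfront therapy. The two dates are set by separate rules, and no rule links them.

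If scan 2 comes well before the first dose, the change to scan 3 includes further response to ADT alone. If it comes after, some upfront response is counted in the scan 1 to scan 2 change, which the model labels as response to hormonal therapy. The two predictors then mean different things in different men.

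The primary test asks what upfront response adds once ADT response is known, and misalignment blurs that contrast. Variation in the gap also adds noise to the predictor and pulls its hazard ratio towards 1. The secondary analysis of response to ADT only is affected too.

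**Working it through.** The plan states no figure for this gap, so there is none to reproduce. One month is taken as 365.25/12 = 30.44 days, and days count from ADT start.

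**Inputs**
- Scan 2: 60.9 ± 7 days, so day 53.9 to day 67.9 (section 5.2.1.2).
- Latest upfront start: before day 91.3 (section 5.2.1.2).
- Scan 3: 53.9 to 67.9 days after the first upfront dose (section 5.2.1.3).

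**1. ADT alone after scan 2** (latest upfront start minus scan 2)
- Scan 2 on target: 91.3 − 60.9 = 30.4 days = 4.3 weeks.
- Scan 2 at the early edge: 91.3 − 53.9 = 37.4 days = 5.3 weeks.
- Scan 2 at the late edge: 91.3 − 67.9 = 23.4 days = 3.3 weeks.

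The limit is strict, so these are upper bounds. On real calendar dates the early-edge maximum is 34 to 37 days.

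**2. Share of the scan 2 to scan 3 interval at the extreme**
- Earliest scan 3: 37.4 / (37.4 + 53.9) = 41%.
- Latest scan 3: 37.4 / (37.4 + 67.9) = 36%.

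**3. Scan 2 after the first dose**
- Upfront start at exactly 2 months, scan 2 at the late edge: 67.9 − 60.9 = 7 days of upfront therapy before scan 2.
- An earlier start gives more. A start on day 28, taken only as an example, puts 53.9 − 28 = 26 to 67.9 − 28 = 40 days before scan 2. Section 5.2.1.2 does not exclude this.

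**4. The two deadlines.** Assume that the baseline scan marks diagnosis and that ADT starts 4 weeks later, the limit in section 5.2.1.1. The section 1 deadline then falls at 91.3 − 28 = day 63 after ADT start, before the scan 2 window closes on day 68.

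**5. Does the model already correct for this?** No. The hormonal-response covariate is the scan 1 to scan 2 change. It cannot remove ADT effect that occurs after scan 2.

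**6. Effect on the hazard ratio.** The documents give neither an ADT-only rate of decline nor a distribution of gaps, so both are assumed.
- Gap uniform over 0 to 5.35 weeks: mean 2.67, mean square 5.35²/3 = 9.53, variance 5.35²/12 = 2.38.
- Decline r of 0.2, 0.4 or 0.6 per week in the plan's units of 10 points (2, 4 or 6 points per week), either common to all men or varying between men with an SD of 50% of the mean.
- From the sample size section: SD 4 and R² 0.75. The variance of the predictor given the other factors is 4² × (1 − 0.75) = 4.
- Added variance: 2.38 r² for a common rate; 1.25 r² × 9.53 − (2.67 r)² for a varying rate.
- Dilution factor λ = 4 / (4 + added variance). Estimated hazard ratio ≈ 1.21^λ.

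| Points per week | Rate | Added variance | λ | Estimated HR |
|---|---|---|---|---|
| 2 | common | 0.095 | 0.977 | 1.205 |
| 2 | varying | 0.191 | 0.954 | 1.200 |
| 4 | common | 0.381 | 0.913 | 1.190 |
| 4 | varying | 0.763 | 0.840 | 1.174 |
| 6 | common | 0.858 | 0.823 | 1.170 |
| 6 | varying | 1.716 | 0.700 | 1.143 |

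Simulated Cox fits (N = 150, 18-month accrual, 48-month cut-off) agree. The estimates are about 1.20-1.21, 1.17-1.20 and 1.14-1.18. Power falls from about 96% with no ADT-only decline to about 95-96%, 90-94% and 85-92%.

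**7. With the gap as a covariate.** A common rate is fully corrected. With varying rates the remaining added variance is 9.53 × (0.5 r)² = 0.095, 0.381 and 0.858, so the estimates are about 1.21, 1.19 and 1.17. In one simulation at 6 points per week with varying rates, power recovered from about 87% to about 92%.

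**The case against.** The plan clearly intends the order ADT, scan 2, upfront therapy. Section 2 describes ADT alone for the first 2-3 months, section 5.2.1.2 is headed as hormonal therapy response, and section 5.7 places the two extra scans within about 4 months, which fits an upfront start near scan 2. A fixed ADT anchor also serves the secondary objective on ADT response, because it standardises that interval. The 5.3-week figure needs two window extremes at once. If scan 2 and the upfront start are each spread evenly over their windows (upfront start at 2-3 months), the simulated hazard ratios at a common rate are 1.21, 1.20 and 1.18, so the dilution is slight. The deadline in section 1 is background, not a study rule.

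Much of this stands. It limits the late-scan problem to about 1 week on the natural reading, and it makes the loss of precision modest unless ADT-only decline is fast. It does not remove the mismatch. An intended order is not a rule, and even with that order kept and scan 2 on target, more than 4 weeks of ADT alone can enter the upfront measure, unadjusted.

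A reader might infer that five weeks of contamination is typical, or that power must fall below the planned 80%. The documents support neither. The first is an extreme. The second needs a decline rate and a gap distribution that the documents do not give, and the lowest power in the simulations relied on here was about 85%.

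**Conclusion.** The point holds as a design weakness that should be corrected, not as a fatal flaw. The timing result rests only on the protocol's windows: up to 4.3 weeks of ADT alone with scan 2 on target, 5.3 weeks at the extremes, and about 1 week in the other direction if ADT alone lasts at least 2 months (more if upfront therapy starts sooner).

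The effect on the hazard ratio and on power rests on assumed decline rates and gap distributions. It is negligible at 2 points per week and noticeable only at 4 to 6. The power figures also assume follow-up to 48 months; fewer events would lower all of them, including the starting 96%.

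The problem of interpretation, whether ADT or upfront therapy carried the signal, is present at any ADT-only decline above zero. It matters most for a study meant to guide the choice of upfront therapy.

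**What to change.** Leave treatment timing as it is. Then:

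1. Within the existing scan 2 window, book the study's scan 2 before the first upfront dose where possible.
2. Record the signed number of days from scan 2 to the first upfront dose, and the days from scan 2 to scan 3.
3. Add the scan-2-to-first-dose gap as a covariate in both Cox models of section 7.1, so that the likelihood ratio test still isolates the upfront response.
4. Keep the section 7.1 analysis set for the primary analysis. Add a sensitivity analysis without men whose scan 2 followed the first dose. Dropping them from the primary analysis would shrink the planned 150, and the documents give no basis for judging by how much.
5. Reconcile section 1 (deadline from diagnosis) with section 5.2.1.2 (deadline from ADT start). Section 3 also times scan 3 from chemotherapy although an ARTA is allowed, and the same edit can align it.

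The cost is a booking instruction, two derived intervals and one extra model term. For men already scanned, the gap can be derived from the scan and treatment dates. The covariate restores the hazard ratio only in part if ADT decline varies between men, so the booking step matters as well.

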5.3 Withdrawal of individual subjects

Subjects can leave the study at any time for any reason if they wish to do so without any consequences.

5.4 Replacement of individual subjects after withdrawal

. Patients who drop out before acquisition of baseline and two response PSMA-PET/CT scans will be replaced. If the endpoint CRPC is not reached due to lost-to-follow-up, patients will be censored at the time of last follow-up.

5.5 Follow-up of subjects withdrawn from treatment

Not applicable. Patients, who drop out of the study, will receive standard of care.

5.6 Premature termination of the study

Treatment and follow-up will proceed as per standard of care in case of study termination.

5.7 Additional findings PSMA PET/CT

Before patients are included in this study they already received a PSMA PET/CT, according to standard of care. During this study two additional standard of care PSMA PET/CT's will be given performed within ±4 months (see also figure 1).

The chance that there will be additional findings ±4 months after the first PSMA PET/CT is very low. If there will be additional findings on the study PSMA PET/CT's, unrelated to prostate cancer, these will be communicated to the treating physician/head practitioner/general practitioner.

6. SAFETY REPORTING

6.1 Temporary halt for reasons of subject safety

In accordance to section 10, subsection 4, of the WMO, the sponsor will suspend the study if there is sufficient ground that continuation of the study will jeopardize subject health or safety. The sponsor will notify the accredited METC without undue delay of a temporary halt including the reason for such an action. The study will be suspended pending a further positive decision by the accredited METC. The investigator will take care that all subjects are kept informed.

6.2 AEs, SAEs and SUSARs

6.2.1 Adverse events (AEs)

Adverse events are defined as any undesirable experience occurring to a subject during the study, whether or not considered related to the study procedures. All adverse events reported spontaneously by the subject or observed by the investigator or her staff will be recorded.

6.2.2 Serious adverse events (SAEs)

A serious adverse event is any untoward medical occurrence or effect that

- results in death;
- is life threatening (at the time of the event);
- requires hospitalization or prolongation of existing inpatients' hospitalization;
- results in persistent or significant disability or incapacity;
- is a congenital anomaly or birth defect; or
- any other important medical event that did not result in any of the outcomes listed above due to medical or surgical intervention but could have been based upon appropriate judgment by the investigator.

An elective hospital admission will not be considered as a serious adverse event.

PSMA PET/CT has not been reported to cause any side effects and is one of the accepted routine imaging options for prostate cancer diagnostics. Since this study concerns an observational study with two standardized PSMA PET/CT examinations, it is not expected that AEs or SAEs occur due to these additions. Only (S)AEs that occur during the PSMA PET/CT procedure will be reported.

The local principal investigator or an authorized delegate will report the SAE to the sponsor without undue delay after obtaining knowledge of the events.

The sponsor will report the recorded SAEs to the accredited METC through line listing at the annual progress report.

6.3 Follow-up of adverse events

All AEs will be followed until they have abated, or until a stable situation has been reached. Depending on the event, follow-up may require additional tests or medical procedures as indicated, and/or referral to the general physician or a medical specialist. SAEs need to be reported till end of study within the Netherlands, as defined in the protocol.

6.4 Data Safety Monitoring Board (DSMB) / Safety Committee

This study is assessed as having a minimal risk for the subject by the principal investigator and is therefore classified as 'low risk, similar to usual care'. Therefore, a DSMB / Safety Committee will not be necessary.

7. STATISTICAL ANALYSIS

7.1 Primary study parameter(s)

The collected data will include nominal, categorical, ordinal and continuous variables.

A predictive model will be constructed. Main parameter is PERCIST PSMA response to upfront therapy. Main outcome is time since diagnosis to development of CRPC. Primary analysis will be the comparison of two Cox proportional hazards models for time to development of CRPC: the first including the six predictive factors (PSA at diagnosis, pathological Gleason score, metastasis volume load, PSA early response, type of upfront therapy, PSMA response to hormonal therapy only), mentioned in section 4.4, and the second including those six variables plus PERCIST PSMA-PET/CT response after start of upfront therapy. The models will be compared using a likelihood ratio test, and the c-statistic will be calculated to estimate the added benefit of PERCIST PSMA response above the known predictors of CRPC.

An intention-to-treat analysis will be performed (i.e. all subjects who actually receive baseline and two follow-up PSMA PET/CT scans.) will be included for analysis, even when treatment is changed early.

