3. STUDY DESIGN

The study is a prospective open-label, non-interventional, non-therapeutic observational cohort study. The study is performed in an outpatient setting. Total study duration will be 48 months.

Multicenter (Netherlands):

- UMC Utrecht, Utrecht (lead);
- St Antonius Hospital, Utrecht / Nieuwegein (external inclusion);
- Meander MC, Amersfoort (external inclusion);
- Amsterdam UMC, Amsterdam (external inclusion).

Patients will be treated with hormonal therapy plus upfront therapy. Indication for upfront therapy and the choice for specific combination will be made at a multidisciplinary meeting. Patients are elected for study participation after prostate cancer has been histologically confirmed and signs of multiple metastases have been confirmed on PSMA-PET/CT-imaging. The definition of multiple / high volume metastasis is: >3 metastatic lesions (any combination of either lymph node metastasis outside of pelvis, bone metastasis, or visceral metastasis). Participating centers will standard use PSMA PET/CT as first imaging choice at suspicion of metastasized disease.

Standardized imaging (Figure 1):

- PSMA-PET/CT:
 - 1. Standard of care PSMA PET/CT: At diagnosis (hormonal therapy needs to be started <4 weeks).
 - 2. Additional PSMA PET/CT: 2 months after start hormonal therapy (+/- 1 week).
 - 3. Additional PSMA PET/CT: 2 months after start of chemotherapy (+/- 1 week).

Patients continue hormonal therapy plus upfront therapy according to standard of care. Follow-up of standard of care consists of monthly outpatient checks, including standard lab tests (i.e. PSA, AF, testosterone, electrolytes, full blood count).

The results of the additional PSMA-PET/CT scans will not be blinded to patients or physicians and will not be used in clinical decision-making.

The primary endpoint is time from start of ADT to CRPC. CRPC is defined by EAU guidelines (Cornford 2020) as:

Castrate serum testosterone <50 ng/dL or 1.7 nmol/L plus either:

- a. Biochemical progression: Three consecutive rises in PSA at least one week apart resulting in two 50% increases over the nadir, and a PSA >2 ng/mL, or:
- b. Radiological progression: The appearance of new lesions: either two or more new bone lesions on skeletal scintigraphy or a soft tissue lesion on CT using RECIST (Response Evaluation Criteria in Solid Tumours) or on (PSMA-)PET/CT-imaging using PERCIST (PET Response Evaluation Criteria In Solid Tumours) (Fanti 2020, Boellaard 2015).

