7.2 Secondary study parameter(s)

- Predictive value of baseline PSMA-PET/CT imaging on time to development of CRPC.
- Predictive value of early response to ADT only on time to development of CRPC.
- Predictive value of early response to ADT combined with upfront therapy on time to development of CRPC.
- Analysis of response in different subgroups of patients: e.g. high versus low tumour load, high versus low PSA, high versus low Gleason score, low versus high age.

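### The set called intention-to-treat in section 7.1 is a three-scan completer set, with no entry time at scan 3 and no other set named for the secondary predictors

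*Combined protocol and SAP*

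**What the plan says.** Section 7.1 (Primary study parameter(s)) defines its analysis set in one sentence: "An intention-to-treat analysis will be performed (i.e. all subjects who actually receive baseline and two follow-up PSMA PET/CT scans". It adds that such men "will be included for analysis, even when treatment is changed early".

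Three other places bear on who is counted:

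- Section 5.4: "Patients who drop out before acquisition of baseline and two response PSMA-PET/CT scans will be replaced". For men lost later, "If the endpoint CRPC is not reached due to lost-to-follow-up, patients will be censored at the time of last follow-up".
- Section 5.5, on follow-up after withdrawal: "Not applicable. Patients, who drop out of the study, will receive standard of care". No study follow-up of these men is described.
- Section 7.2 lists secondary analyses, including "Predictive value of baseline PSMA-PET/CT imaging on time to development of CRPC" and the predictive value of response to ADT alone. It names no analysis set.

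The time origin is given in two ways. Section 3 says "The primary endpoint is time from start of ADT to CRPC", and section 5.1.1 agrees. Section 7.1 says "Main outcome is time since diagnosis to development of CRPC". Neither version mentions a landmark or delayed entry.

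**The concern.** Intention-to-treat normally means that nobody leaves the analysis because of what happened after entry. Here a man must reach, and attend, a scan several months after his clock has started. A man who dies, becomes too ill or withdraws before scan 3 is left out and replaced by one who got that far.

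Three things are at stake:

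1. The report would carry a label that its analysis set does not support.
2. Time between the origin and scan 3 counts as event-free follow-up for every man whose inclusion depended on getting through it. That lengthens any median or absolute risk read from the set.
3. The baseline-scan analysis needs only scan 1, and the ADT-response analysis only scans 1 and 2. If both use the section 7.1 set, men are dropped for events after the predictor was measured. The results would then describe men who reach scan 3, whereas section 2 aims at newly diagnosed men.

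**Working it through.** **Plan's own figure.** The documents give no drop-out rate and no expected number of early failures. The nearest figure is the sample size in section 4.2. With events = (1.960 + 0.842)² / (SD² × ln(HR)² × (1 − R²)), HR 1.2, SD 4 and R² 0.80, this gives 73.8 events. At an event probability of 0.5 that is N = 148, close to the stated 150. The R² of 0.75 in the text gives 59.0 events and N = 119. So 150 corresponds to about 75 events by 24 months, with no allowance for men missing a scan.

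**When membership is known.** ADT alone runs for 2 to 3 months (sections 2 and 5.2.1.2), and scan 3 follows 2 months after upfront therapy starts, give or take a week (section 5.2.1.3). Scan 3 therefore falls at L of about 2 + 2 = 4 to 3 + 2 + 0.25 = 5.25 months after ADT start.

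**Median in the completer set.** Let F be the probability of CRPC before L, f the share of those men who miss a scan and are lost, and λ the hazard. For t beyond L, survival among those kept is S(t) / (1 − fF). The apparent median is therefore the true median + [−ln(1 − fF)] / λ. With f = 1 and a constant hazard, this is the true median + L. Both f and the shape of the hazard are assumptions.

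- Constant hazard, median 24 months (section 4.2): λ = ln 2 / 24 = 0.0289 per month.
- Constant hazard, median 18 months (section 1): λ = ln 2 / 18 = 0.0385.
- No CRPC before month 3, median 24 months: λ = ln 2 / 21 = 0.0330 afterwards, so F = 1 − exp(−λ(L − 3)). The reason for this case is that biochemical CRPC needs three consecutive PSA rises and PSA is checked monthly (section 3).

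| Assumption | F (L = 4 to 5.25) | Apparent median, f = 0 | f = 0.5 | f = 1 |
|---|---|---|---|---|
| Constant hazard, 24 months | 10.9% to 14.1% | 24 | 25.9 to 26.5 | 28.0 to 29.25 |
| Constant hazard, 18 months | 14.3% to 18.3% | 18 | 19.9 to 20.5 | 22.0 to 23.25 |
| None before month 3, 24 months | 3.2% to 7.2% | 24 | 24.5 to 25.1 | 25.0 to 26.25 |

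**Early failures replaced.** To obtain 150 completers with f = 1, the number replaced is 150 × F / (1 − F). This gives 5 to 12 with none before month 3, 18 to 25 under a constant hazard with median 24, and 25 to 34 with median 18.

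**Effect on the primary hazard ratio.** In 600 simulated trials of 150 men (HR 1.2 per unit, residual SD 2, scan 3 at 4 to 5 months), the mean estimated hazard ratio was 1.203 in all enrolled, 1.203 in completers with f = 1, and 1.204 in completers with delayed entry. Simulated medians were 23.8 months in all enrolled, 26.2 with f = 0.5 and 28.6 with f = 1, in line with the formula. The likelihood ratio test and the c-statistic were not checked separately for bias.

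**Events left after a landmark.** Among 150 men event-free at scan 3, with a 24-month median, events by month 24 number 150 × (1 − exp(−λ(24 − L))). That is 63 to 66 under a constant hazard and 69 to 72 with none before month 3, against 75 in the plan.

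**The case against.** The strongest reply is that the bias lies in something the plan does not set out to report. The primary analysis is a likelihood ratio test of two nested Cox models with a c-statistic. No median time to CRPC or absolute risk by PET group is planned, and the hazard ratio barely moves. This stands, and it is why the point does not threaten the primary test.

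It is also fair that the primary predictor is a change between scans 2 and 3 and is undefined without both. Restricting the primary models to men with those scans is inherent to the question and is not a fault in itself.

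A reader might infer that all early failures vanish from the study. The documents do not say so. Section 5.4 replaces men who drop out, not men who progress. Section 3 sends progression to multidisciplinary review, and section 7.1 keeps men whose treatment changes early if they were scanned. Only early failures who also miss a scan are lost, and that share is unstated.

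A reader might also take a shift from 24 to 29 months as the expected size. That needs every early failure to be lost and a constant hazard from day 0. The PSA rule makes very early biochemical CRPC unlikely, although radiological progression could come sooner. Death is not a CRPC event, so these figures do not measure losses through death.

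Finally, section 7.2 does not say that its analyses use the three-scan set. What is established is that no other set is named, not that men will be excluded.

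**Conclusion.** The point holds in limited form. The intention-to-treat label is wrong whatever the drop-out rate. The clock starts before membership of the set can be known, and the set for the baseline-scan and ADT-response analyses is unspecified.

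With a 24-month median, the upward bias in any reported median time to CRPC runs from near zero (early failures still scanned), through about 1 to 2 months (all lost, none before month 3), to at most about 4 to 5 months (all lost, constant hazard). The documents do not allow a choice within that range. The primary hazard ratio is little affected if hazards are proportional. The consequence for the primary result is mainly one of scope: it applies to men who reach scan 3. In addition, a CRPC event before scan 3 in a scanned man would be predicted from a later measurement.

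This should be corrected before analysis, but it does not invalidate the design.

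**What to change.** 1. In section 7.1, replace the intention-to-treat label with three-scan evaluable set.
2. For the two primary Cox models, start time at scan 3 (landmark) or keep the chosen origin with delayed entry at scan 3. Report men with CRPC before scan 3 separately. Renaming the set a landmark set without moving the clock would not be enough. Reconcile the origin (ADT start or diagnosis) at the same time.
3. In section 7.2, name the sets: the baseline-scan predictor in all enrolled men with scan 1; ADT response in all men with scans 1 and 2, counted from scan 2. Include replaced men in both.
4. In sections 5.4 and 5.5, keep collecting routine PSA and testosterone results for replaced men unless they withdraw consent.
5. Report a flow table with the reasons for a missing scan 2 or 3. If a median time to CRPC is given, take it from all enrolled men.

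The cost is the change of wording, extraction of routine follow-up data for replaced men (about 5 to 30 early failures, up to 34 in the most extreme case above, plus any other drop-outs), and slightly fewer events in the primary models. No extra scans or enrolment are needed.
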